5 GENERAL CONSIDERATIONS

Formats and layouts of tables, listings, and figures (TLF) will be provided in a separate document (output general layout is described in [Appendices](#)

[Appendix 1](#)).

	STATISTICAL ANALYSIS PLAN, Version 3.0
Protocol Number: ARQ-151-311	Sponsor: Arcutis Biotherapeutics, Inc.

5.1 Sample Size

There are approximately 650 subjects planned for this study. In order to have the desired power for the secondary endpoint of vIGA-AD Success in subjects with a vIGA-AD score of ‘Moderate’ at randomization, approximately 490 of the subjects to be accrued will have vIGA-AD score of ‘Moderate’ at randomization. Randomization will be stratified by vIGA-AD score (‘Mild’ vs. ‘Moderate’) and by study site.

The sample size of 650 subjects provides approximately 95% power to detect an overall 15% difference (Odds Ratio = 2.1) between treatment groups on vIGA-AD success at Week 4 at $\alpha=0.05$ using a 2-sided stratified Cochran-Mantel-Haenszel (CMH) test. The results from a recent Phase 2 study (ARQ-151-212) of Roflumilast cream 0.15% compared to vehicle treatment were used to estimate the treatment difference. Specifically, in the Phase 2 trial, approximately 37% of subjects demonstrated vIGA-AD Success at Week 4 in the ARQ-151 0.15% group compared to 22% in the vehicle group. The sample size of 490 also provides approximately 90% power to detect an overall 17% difference (Odds Ratio = 2.1) between treatment groups (28% of vIGA-AD Success at Week 4 in vehicle treatment) on vIGA-AD Success at Week 4 among subjects with vIGA-AD score ‘moderate’ at randomization. The same testing method, the stratified CMH test, will be used as for the primary endpoint.

To control for familywise type I error at level of 0.05, the secondary endpoint of vIGA-AD Success at Week 4 in subjects with vIGA-AD of ‘Moderate’ at randomization will only be tested if the primary endpoint demonstrates statistical significance. In addition, the remaining secondary endpoints will be inferentially tested only if the primary and secondary endpoint (vIGA-AD Success at Week 4 for subjects with vIGA-AD score of ‘Moderate’ at randomization) comparisons are statistically significant using the hierarchical testing procedure by partitioning of alpha (see Section 6.5 for more details).

5.2 Baseline

Unless otherwise specified, baseline value will be defined as the last non-missing assessment prior to or concurrently with the first study treatment dosing* (including unscheduled/retest assessments). If the last non-missing assessment is performed on the same date as the first study treatment administration* and time is not available, it is assumed that the assessment took place prior to IP application*, per study site training, and the assessment will be considered as baseline, except for adverse events (AEs) and medications starting on the first study treatment dose administration date which will be considered postbaseline.

Average weekly baseline WI-NRS is defined as the average of all non-missing scores reported during the last 7 days prior to treatment* if at least 4 of 7 evaluable daily WI-NRS questionnaires

	STATISTICAL ANALYSIS PLAN, Version 3.0
Protocol Number: ARQ-151-311	Sponsor: Arcutis Biotherapeutics, Inc.

available. Daily baseline WI-NRS is defined as the last non-missing assessment prior to or concurrently with the first study treatment dosing*. Day 1 WI-NRS score will be used to calculate the value for week 1 only when it is collected after the application of the first study drug*. If Day 1 WI-NRS score is collected prior to or concurrently with the application of the first study drug*, then the Day 1 WI-NRS score will be included in baseline calculation.

For investigator/subject tolerability assessments, baseline is derived as the measurement taken on the day of first application of study drug*.

* For randomized subjects who discontinued study before the first application of study treatment, the date of randomization will be considered instead of the date of the first application of study treatment.

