2 STUDY OBJECTIVES AND ENDPOINTS

OBJECTIVES	ENDPOINTS
Efficacy	
To assess the efficacy of Roflumilast (also known as ARQ-151) cream 0.15% vs vehicle administered once daily	
Primary efficacy endpoint:
 
 • Validated Investigator Global Assessment scale for Atopic Dermatitis (vIGA-AD) Success, defined as a vIGA-AD score of 'clear' (0) or 'almost clear' (1)

	STATISTICAL ANALYSIS PLAN, Version 3.0
Protocol Number: ARQ-151-311	Sponsor: Arcutis Biotherapeutics, Inc.

OBJECTIVES	ENDPOINTS
(QD) x 4 weeks to individuals 6 years of age and older with atopic dermatitis (AD).	
plus at least a 2-grade improvement from Baseline at Week 4
 
Secondary efficacy endpoints:
 
 • In subjects with a vIGA-AD score of 'Moderate' at randomization, vIGA-AD Success at Week 4 • In subjects ≥ 12 years old with baseline Worst Itch - Numeric Rating Score (WI-NRS) ≥ 4, achievement of at least a 4-point reduction on the WI-NRS at Week 4 • In subjects ≥ 12 years old with baseline WI-NRS ≥ 4, achievement of at least a 4-point reduction on the WI-NRS at Week 2 • In subjects ≥ 12 years old with baseline WI-NRS ≥ 4, achievement of at least a 4-point reduction on the WI-NRS at Week 1 • Achievement of at least a 75% reduction in the Eczema Area and Severity Index (EASI-75) at Week 4 • vIGA-AD of 'clear' or 'almost clear' at Week 4 • vIGA-AD Success at Week 2 • vIGA-AD Success at Week 1 • vIGA-AD of 'clear' or 'almost clear' at Week 2 • vIGA-AD of 'clear' or 'almost clear' at Week 1 
Exploratory efficacy endpoints:
 
 • Other continuous efficacy endpoints include change and percent change in average weekly WI-NRS and daily WI-NRS, EASI, % body surface area (BSA) affected by AD, Dermatology Life Quality Index (CDLQI/DLQI), the Dermatitis Family Impact (DFI), Scoring Atopic Dermatitis (SCORAD), and Patient-oriented Eczema Measure (POEM) at Week 1, Week 2 and Week 4. • Other categorical efficacy endpoints include EASI-50, EASI-90, EASI-100, and vIGA-AD of 'clear' at Week 4
Safety	

	STATISTICAL ANALYSIS PLAN, Version 3.0
Protocol Number: ARQ-151-311	Sponsor: Arcutis Biotherapeutics, Inc.

OBJECTIVES	ENDPOINTS

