5.6 Descriptive Statistics

All continuous variables will be summarized by presenting the number of subjects, mean, standard deviation (SD), median, Q1, Q3, minimum, and maximum. For PK endpoints, geometric statistics including geometric mean and coefficient of variation (CV) will also be provided.

Categorical variables will be presented as frequencies and percentages.

Summary tables will be presented by visit, when applicable.

Change from baseline will be calculated as:

	STATISTICAL ANALYSIS PLAN, Version 3.0
Protocol Number: ARQ-151-311	Sponsor: Arcutis Biotherapeutics, Inc.

Assessment value at postbaseline visit X – baseline value.

Percent change from baseline will be calculated as:

$$(\text{Assessment value at postbaseline visit X} - \text{baseline value}) \times 100\% / (\text{baseline value})$$

Percent change from baseline will be missing in situation where baseline value equals to 0.

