- The SCORAD is a clinical tool to assess the severity (i.e., extent, intensity) of AD as objectively as possible. First, the overall %BSA affected by AD is evaluated (from 0% to 100%, where a subject's palm represents 1% of his/her total BSA). Secondly, the AD severity is evaluated based on 6 items (erythema, edema/papulation, oozing/crusts, excoriation, lichenification, and dryness) graded using a 4-point scale (half steps are not allowed): 0 (absence), 1 (mild), 2 (moderate), and 3 (severe). Lastly, 2 subjective items (loss of sleep and intensity of pruritus) are evaluated by having the subject indicates on a 10.0 cm visual analog scale (VAS) the point corresponding to the average value over the last 3 days (0 cm = none to 10 cm= maximum).
- The POEM is a tool used for monitoring atopic eczema severity. It focuses on the illness as experienced by the subject. It consists of a 5-point scale measuring the frequency of each of 7 AD symptoms (i.e., dryness, itching, flaking, cracking, sleep loss, bleeding, and weeping) over the past week scored from 0 (no days), 1 (1 to 2 days), 2 (3 to 4 days), 3 (5 to 6 days), and 4 (every day).

For the continuous exploratory efficacy endpoints of change and percent from baseline in average weekly WI-NRS, EASI total score, % BSA, DLQI/CDLQI score, DFI score, SCORAD score, and POEM score at Week 1, Week 2, and Week 4, descriptive statistics for the score, change from baseline and percent change from baseline will be presented by visit and treatment group based on observed data in the ITT population. Descriptive statistics will also be presented similarly for the average weekly WI-NRS at Week 3. For the continuous efficacy exploratory endpoint of daily WI-NRS, descriptive statistics will be presented similarly but on a daily basis instead of a weekly basis. Additionally, a plot of the mean (and standard error) daily WI-NRS scores over time for each treatment group will also be provided based on observed data. A similar plot will be provided for the percent change from baseline in daily WI-NRS.

	STATISTICAL ANALYSIS PLAN, Version 3.0
Protocol Number: ARQ-151-311	Sponsor: Arcutis Biotherapeutics, Inc.

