For each categorical exploratory efficacy endpoint, count and percentages of subjects meeting the criteria for an exploratory efficacy endpoint will be presented by visit and treatment group based on observed data in the ITT population along with a 95% Wilson CI. Additionally, count and percentage of subjects meeting the criteria for vIGA-AD of Clear (0), EASI-50, EASI-90, and EASI-100 at Week 1 and Week 2 will also be presented by visit and treatment group based on observed data in the ITT population along with a 95% Wilson CI.

Continuous exploratory efficacy endpoints will be analyzed at Week 1, Week 2, and Week 4 and for daily WI-NRS assessments using an analysis of covariance (ANCOVA) with the factors of treatment, two stratification variables (pooled study site and randomized vIGA-AD score), and baseline of the variable under analysis as covariate. Statistical comparisons between the treatment groups will be obtained using contrasts. The Least Square (LS) mean and its standard error, difference in LS means between treatment group (i.e., active - vehicle), its standard error and associated 95% confidence interval, and p-value for difference from vehicle will be presented at each visit. These analyses will be performed based on observed data in the ITT population.

Categorical exploratory efficacy endpoints at Weeks 1, 2, and 4 will be analyzed using a CMH test adjusted for the two stratification variables (pooled study site and randomized vIGA-AD score). Common MH odds ratio, common MH proportion difference and their common associated 95% CI, adjusted for the randomization factors, will be provided. The p-value will be from a CMH test for the common MH odds ratio, unless the common MH odds ratio is not estimable. In such circumstances, the p-value will be from a MH test for the common MH proportion difference.

The analysis of these endpoints will be performed on the observed data with no imputation. The p-values will be nominal as no formal inferential testing will be done on exploratory efficacy endpoints.

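### The daily itch ANCOVA adjusts for one pre-dose score only; adding the 7-day pre-treatment mean as a second covariate is a free gain in precision for an exploratory endpoint, and mean percent change needs medians

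*SAP*

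**What the plan says.** SAP 5.2 defines two itch baselines. One is a weekly value: "Average weekly baseline WI-NRS is defined as the average of all non-missing scores reported during the last 7 days prior to treatment", subject to at least 4 of 7 scores being present. The other, for the daily analysis, is a single score: "Daily baseline WI-NRS is defined as the last non-missing assessment prior to or concurrently with the first study treatment dosing".

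SAP 2 lists the affected outcomes among the exploratory endpoints: "Other continuous efficacy endpoints include change and percent change in average weekly WI-NRS and daily WI-NRS, EASI". SAP 12.3 analyses them by ANCOVA with treatment, "two stratification variables (pooled study site and randomized vIGA-AD score), and baseline of the variable under analysis as covariate". It does not name the baseline used for daily WI-NRS; taken with 5.2, it is the single score. SAP 12.3 also asks for a plot of mean and standard error of the daily score, and adds: "A similar plot will be provided for the percent change from baseline in daily WI-NRS".

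On percent change, SAP 5.6 says: "Percent change from baseline will be missing in situation where baseline value equals to 0". On the analysis set, SAP 12.3 says: "These analyses will be performed based on observed data in the ITT population". The minimum baseline of 4 in SAP 4.6 therefore does not apply here, and no inclusion criterion in Protocol 4.5.1 sets a minimum itch score.

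**The concern.** A single 0-10 itch score mixes the subject's usual level with that day's fluctuation. A mean of up to seven scores usually predicts later itch better, so leaving it out of the model usually gives away precision that has already been collected.

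Percent change raises a different problem. A low score by chance makes a small denominator and a large positive percent change; a high score by chance gives only a modest negative one. Take a subject whose true level stays at 3 and whose baseline reads 2 or 4 with equal chance. The mean absolute change is 0, but the mean percent change is (50% - 25%)/2 = +12.5%. At stake is how well the daily curves and their nominal p-values describe the itch response.

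**Working it through.** **Inputs.** From the documents: about 650 subjects (SAP 5.1), the two baseline definitions, the ANCOVA covariates and the zero-baseline rule. The plan states no standard deviation, autocorrelation or power for daily WI-NRS, so there is no plan figure to reproduce. All variance inputs below are assumptions.

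**Precision.** Set the variance of a daily score to 1 and split it into a stable subject part a, an autoregressive part b with lag-1 correlation φ, and independent day noise 1 - a - b. Scores on days s and t then have covariance a + bφ^|s-t|. ANCOVA residual variance is proportional to 1 - r², where r is the correlation of the day-t score with the covariate. The SE ratio (single day over 7-day mean) is √[(1 - r₁²)/(1 - r₇²)]. A ratio above 1 favours the 7-day mean.

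*Independent noise, a = 0.7, b = 0.* Single day: 1 - 0.7² = 0.51. Variance of the 7-day mean: 0.7 + 0.3/7 = 0.743, so r₇² = 0.49/0.743 = 0.660 and 1 - r₇² = 0.340. Ratio √(0.51/0.340) = 1.224 on every day; 650 subjects then act like 650/1.224² = 434.

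*Strong short-term correlation, a = b = 0.5, φ = 0.8, day 1.* Single day: r₁ = 0.5 + 0.5 × 0.8 = 0.90, so 1 - r₁² = 0.19. For the 7-day mean, the covariance with the day-1 score is 0.726 and the variance 0.820, so r₇² = 0.726²/0.820 = 0.642 and 1 - r₇² = 0.358. Ratio √(0.19/0.358) = 0.729: the single day is clearly better on that day.

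| Assumed structure | Day 1 | Day 28 | Mean, days 1-28 | Single day vs both covariates, mean |
|---|---|---|---|---|
| a 0.5, noise 0.5 | 1.155 | 1.155 | 1.155 | 1.155 |
| a 0.7, noise 0.3 | 1.224 | 1.224 | 1.224 | 1.224 |
| slow drift: b 0.7 at φ 0.98, noise 0.3 | 1.132 | 1.024 | 1.059 | 1.063 |
| a 0.5, b 0.2 at 0.6, noise 0.3 | 1.075 | 1.117 | 1.113 | 1.115 |
| a 0.5, b 0.4 at 0.8, noise 0.1 | 0.906 | 1.054 | 1.038 | 1.051 |
| a 0.5, b 0.5 at 0.8, no noise | 0.729 | 1.038 | 1.008 | 1.033 |

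These rows span 1-22% on average. Two edge cases fall outside: a = 0.9 with independent noise gives 1.291, and b = 0.9 at φ = 0.95 with no stable part gives 0.979 on average (0.895 on day 1). With both covariates entered, the single-day SE was at least as high on every day in every structure, edge cases included.

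**Percent change.** Integer 0-10 scores were simulated with no true change, baseline 0 set to missing, mean 4-6, between-subject SD 2.0-2.3, day-to-day SD 0.8-2.0 and lag-1 autocorrelation 0 or 0.6.

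- Single-day baseline: mean +3% to +16% with independent noise; +1.4% to +7% on day 1 with autocorrelation 0.6.
- 7-day baseline: about +1% to +8% with independent noise, but up to +24.4% on day 7 with autocorrelation 0.6 and mean 4, where the single day gave +14.7%.
- Median: about 0 with either baseline. Mean absolute change: about 0.
- Only subjects with a 7-day mean of at least 4: dividing by the single score still gave +0.4% to +12.5%; dividing by the 7-day mean gave -0.1% to -6.9%.

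**The case against.** The plan matches each outcome to a baseline of its own kind, weekly to weekly and daily to daily. That is defensible, and randomization keeps the ANCOVA treatment difference unbiased with either covariate. The endpoint is exploratory with nominal p-values. Family 1 uses weekly averages throughout, including Week 1 (SAP 12.2). Summary tables already carry medians and quartiles (SAP 5.6). Filling in the weekly baseline when fewer than 4 scores exist would also clash with the 4-of-7 rule.

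All of this stands, and it sets the weight of the point. It is no reason to leave a collected covariate out of the model: the addition below keeps the daily baseline and does not touch the 4-of-7 rule. The tabulated medians do not help the plot, which shows means.

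A reader might infer that the loss is largest on the first days and so weakens evidence on speed of onset. The documents do not support that. Under independent noise the loss is equal on all days; only slow drift makes it largest early; under short-term autocorrelation it reverses early. Nor does the SAP say that the daily analysis is there to establish onset. A reader might also infer that replacing the single score by the 7-day mean cures the percent-change shift. It does not: the cause is small denominators, and the swap alone can enlarge the shift.

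**Conclusion.** The point holds as a free improvement to an exploratory analysis. On the reading that the daily ANCOVA uses the single score, its SE is about 1-22% higher than with the 7-day mean, averaged over days 1-28, in the structures tabulated; edge cases run from 2% lower to 29% higher. This rests wholly on assumed correlations. Larger figures, such as a residual variance 29-36% lower with the 7-day mean, need independent day-to-day noise and should not be quoted as the expected gain. What does not depend on the structure is that adding the second covariate cannot raise the population residual variance.

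Mean percent change is shifted upward when nothing has changed, by roughly 1-16% with the planned baseline under the assumptions above. With no treatment effect the shift is the same in both arms. Neither the absolute treatment difference nor any alpha-controlled endpoint is compromised.

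**What to change.** 1. In SAP 12.3, name the covariates of the daily WI-NRS ANCOVA: the daily baseline from 5.2 plus the mean of the available daily scores in the last 7 days before treatment. Label the mean as a covariate for this analysis only, so that the 4-of-7 rule for the average weekly baseline stays as it is.
2. For daily percent change, plot medians with quartiles. The alternative is to limit the plot to subjects with an average weekly baseline of at least 4. In that case divide by the weekly average too, since the restriction alone left up to +12.5% in the simulation; a small downward shift then remains, so medians are cleaner.

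The cost is SAP wording before unblinding, one model degree of freedom and one changed figure. No new data are needed.

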5.3 Reference Start Date and Analysis Day

Analysis day will be calculated from the first study treatment administration date* and will be used to derive start/end day of assessments or events.

Analysis day = (Date of event – Date of first dose administration*) + 1 if date of event is on or after the date of first dose administration of study treatment*;
 = (Date of event – Date of first dose administration*) if date of event is before the date of first dose administration of study treatment*.

In the situation where the assessment/event date is partial or missing, analysis day will be missing.

* For randomized subjects who discontinued study before the first application of study treatment, the date of randomization will be considered instead of the date of the first application of study treatment.

5.4 Windowing Conventions

Visits will be analysed as scheduled. Unscheduled, early termination visits, and/or retest measurements will only be included if a scheduled measurement is not available and the early termination or unscheduled/retest measurement falls within the analysis visit windows as described in [Table 2](#), [Table 3](#), and [Table 4](#) when appropriate. Unscheduled/retest measurements will be listed.

If there is more than one assessment for a given timepoint and analysis visit when a scheduled measurement is not available, the assessment closest to the target day will be considered.

	STATISTICAL ANALYSIS PLAN, Version 3.0
Protocol Number: ARQ-151-311	Sponsor: Arcutis Biotherapeutics, Inc.

Table 2 Analysis Visit Windows for Efficacy Endpoints, Vital Signs, CDI-2, PHQ-8, PHQ-A, C-SSRS and Local Tolerability Assessment

Analysis Visit	Target Day	Lower Limit	Upper Limit
Week 1	8	2	11
Week 2	15	12	22
Week 4	29	23	43

Table 3 Analysis Visit Windows for Clinical Laboratory, Physical Examination and PK assessment

Analysis Visit	Target Day	Lower Limit	Upper Limit
Week 4	29	23	43

Table 4 Windows for the derivation of Average Weekly WI-NRS

Days for calculation of weekly average	Week (Derived)
(-7, -1)*	Baseline
(1, 7)*	Week 1
(8, 14)	Week 2
(15, 21)	Week 3
(22, 28)	Week 4

* Day 1 WI-NRS score will be used to calculate the value for week 1 only when it is collected after the application of the first study drug (randomization for randomized subjects who were never treated with study drug). If Day 1 WI-NRS score is collected prior to or concurrently with the application of the first study drug (randomization for randomized subjects who were never treated with study drug), then the Day 1 WI-NRS score will be included in baseline calculation.

Note: With the caveat described in footnote **, if more than one WI-NRS score is available on the same day, the worst score of the day will be considered in the analyses.

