5.5. Early Termination Visit

If a subject is withdrawn or wishes to exit the study, a termination visit will be scheduled. This visit should include the procedures and assessments that would be performed at the Week 4/Day 29 visit.

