6.6. Safety Analysis

Descriptive statistics will be calculated for quantitative safety data and frequency counts will be compiled for classification of qualitative safety data. The safety population will be used for these analyses.

Adverse Events:

The subject incidence of treatment-emergent adverse events (TEAE) will be summarized overall, by severity, and by attribution.

Clinical Laboratory Results:

Shifts in clinical laboratory parameters from baseline to worst post-baseline grade will be provided.

Vital Signs:

The subject incidence of >5% weight loss or gain on study will be provided, as well as whether weight loss was explained or unexplained.

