5.8 Handling of Retests, Unscheduled Visits, and Early Termination Data

Retests measurements, Unscheduled measurements, and ET visit assessments will be included in analysis and be summarized via analysis visit windowing according to the windowing conventions in section 5.4.

All data from retest, unscheduled measurements and ET visit assessments will be listed.

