13.2 Clinical Laboratory

Descriptive statistics for the observed values in chemistry, hematology, and quantitative urinalysis, change from baseline and percent change from baseline values will be presented by treatment group at each scheduled visit. For qualitative urinalysis data, the number and percentage of the subjects for each level of result by treatment at each scheduled visit will be provided.

Shift tables from baseline to each postbaseline assessments describing shifts to out-of-normal range will be provided for chemistry, hematology, and qualitative urinalysis. Only subjects with a baseline result and a result at the specified visit for the parameter will be considered.

Listings of abnormal laboratory will be provided for each parameter where a subject had at least one abnormal result.

Laboratory data will be presented in SI units.

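### Laboratory results from early-termination, unscheduled or retest samples outside Days 23-43, or superseded by a scheduled Week 4 value, reach only listings, and the SAP has no worst-post-baseline laboratory table

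*SAP*

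**What the plan says.** **Collection.** In the schedules of both documents, the only scheduled post-baseline laboratory draw is at Week 4/Day 29 or early termination. On the early-termination visit, Protocol 5.5 says: "This visit should include the procedures and assessments that would be performed at the Week 4/Day 29 visit". Protocol 5.1.6 allows laboratory tests at unscheduled times at the Investigator's discretion, and Protocol 5.6 names repeat testing after an abnormal result as a reason for an unscheduled visit.

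**Windowing.** SAP 5.4 sets two conditions. The first is that "Unscheduled, early termination visits, and/or retest measurements will only be included if a scheduled measurement is not available". The second is that "the early termination or unscheduled/retest measurement falls within the analysis visit windows". If several such values compete, "the assessment closest to the target day will be considered". The laboratory window is in "Table 3 Analysis Visit Windows for Clinical Laboratory, Physical Examination and PK assessment", which has one row: Week 4, target Day 29, limits Day 23 and Day 43. SAP 5.8 repeats the principle: "Retests measurements, Unscheduled measurements, and ET visit assessments will be included in analysis and be summarized via analysis visit windowing". It adds that all of these data will be listed.

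**Tables.** SAP 13.2 plans descriptive statistics at each scheduled visit and shift tables against the normal range. For the shift tables, "Only subjects with a baseline result and a result at the specified visit for the parameter will be considered". It also plans listings of abnormal results. The supplied protocol, in section 6.6 and again in 6.8, plans something different: "Shifts in clinical laboratory parameters from baseline to worst post-baseline grade will be provided". Protocol 6.12 separately plans a shift table against the normal range.

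**The concern.** Because nothing is scheduled between Day 1 and Week 4, every laboratory result from Days 2-22 is an early-termination, unscheduled or retest sample, and Table 3 has no window for those days. These samples are unlikely to be a random subset. They arise because a subject is leaving or because someone wanted a result checked. Protocol 5.9 ties one treatment-stopping rule to a Grade 3 laboratory abnormality confirmed by a repeat sample. If that happens before Day 23, neither the first nor the confirming value can appear in a laboratory table. If the subject stops treatment but stays in the study, the value tabulated is the Week 4 one, taken off drug.

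At stake is whether the by-arm laboratory tables describe the safety population or mainly those with a Week 4 value. Listings keep the individual values but give no rates and no comparison between arms.

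**Working it through.** The plan states no figure on this point, so there is none to reproduce. The check applies the SAP's own rules.

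**1. Day coverage (SAP 5.4).**
- Table 2 (vital signs, depression and suicidality scales, efficacy, local tolerability): Days 2-11, 12-22 and 23-43, so 10 + 11 + 21 = 42 days without a gap.
- Table 3 (laboratory): Days 23-43, so 21 days.
- Difference: Days 2-22, 21 days. Of the 28 days from Day 2 to Day 29, 21 have no laboratory window and 7 do.

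**2. The two conditions applied.** A non-scheduled value enters only if there is no scheduled Week 4 value and 23 ≤ day ≤ 43.

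| Day of early-termination, unscheduled or retest sample | Scheduled Week 4 value? | In summary and shift table? |
|---|---|---|
| 10 | No | No |
| 22 | No | No |
| 23 | No | Yes |
| 25 | No | Yes |
| 25 | Yes | No |
| 40 | No | Yes |
| 44 | No | No |

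The exclusion is therefore partial and depends on timing. Where a choice is made, it goes to the scheduled value or the value nearest Day 29, never to the worst one.

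**3. Does SAP 13.2 widen this?** Its mention of each post-baseline assessment could be read as reaching every sample. Its next sentence restricts the table to a result at the specified visit, and 5.4 and 5.8 route non-scheduled values through the windows. The by-visit reading is the better supported one.

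**4. Asymmetry with baseline.** SAP 5.2 counts unscheduled and retest values toward baseline. After baseline, the same kinds of value count only under the two conditions above.

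**5. Grade and worst value.** Supplied protocol 6.6 and 6.8: worst post-baseline, by grade. SAP 13.2: one value per visit, against the normal range. The range-based table matches Protocol 6.12. The worst-grade table has no counterpart in the SAP.

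**6. How the size would behave (assumed rates only).** Let *e* be the share of subjects whose only post-baseline result is before Day 23, *a* their abnormality rate, and *b* the rate in everyone else. The table shows *b*; the rate over all is *ea* + (1 − *e*)*b*; the shortfall is *e*(*a* − *b*).
- *a* = *b*: shortfall 0, whatever *e* is.
- *e* = 5%, *a* = 10%, *b* = 2%: 0.5% + 1.9% = 2.4%, shortfall 0.4 percentage points.
- *e* = 10%, same *a* and *b*: 1.0% + 1.8% = 2.8%, shortfall 0.8 percentage points.

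With 650 × 2/3 ≈ 433 active subjects, 5% to 10% would be about 22 to 43. Under Amendment 2 the number is smaller, because SAP Table 1, footnote b, limits laboratory sampling after screening to subjects aged 12 or older.

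**The case against.** **What stands on the other side.** The safety analysis is descriptive (SAP 13). All early-termination, unscheduled and retest results are listed, and abnormal results are listed again. Abnormalities with clinical sequelae, or needing therapy, are handled as adverse events under Protocol 5.7.1, and treatment-emergent events are tabulated by arm with no visit window. For a retest after an abnormal scheduled Week 4 result, the rule is conservative: a normal retest cannot replace the abnormal value. A subject who stops treatment but stays in the study still has Week 4 laboratory tests. These facts make the point a modest one. They do not remove it: Protocol 5.7.1 generally keeps findings judged not clinically significant out of the adverse event record, and where applicable records the sequelae rather than the laboratory abnormality.

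**Stronger readings that the documents do not support.**
- *That all early-termination and unscheduled laboratory results are left out of every table.* The second half of the SAP 5.4 rule admits values within Days 23-43 when no scheduled value exists, and SAP 5.8 confirms it.
- *That the SAP silently departs from its protocol.* The SAP follows Amendment 4, and only the Original version was supplied. SAP 3.5 cites as original text a per-protocol population that the supplied protocol does not contain, so it is comparing against a different text. Whether Amendment 4 keeps the worst-grade shift is unknown.
- *That weight, PHQ, CDI-2 and C-SSRS results suffer the same loss.* Table 2 covers Days 2-43 without a gap, Protocol 5.6 does not list these among the items collected at unscheduled visits, SAP 13.3 summarises weight change over the whole study, and SAP 13.7 counts a positive C-SSRS answer at any point, although by visit.
- *That a percentage understatement can be stated.* The rates in step 6 of the working are assumptions, and equal rates give zero.

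**Conclusion.** The point holds in a limited form. Early-termination, unscheduled and retest laboratory results before Day 23 or after Day 43, and those within Days 23-43 that compete with a scheduled Week 4 value, enter no by-arm laboratory summary or shift table. No worst-post-baseline laboratory table fills the gap. This part rests on SAP 5.4, 5.8 and 13.2 alone. The mismatch with a promised worst-grade shift is shown only against the Original protocol.

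The likely direction is understatement of abnormalities in subjects who leave early or are tested off schedule, on the plausible but undocumented assumption that they have more of them. The documents give neither an early-termination rate nor an unscheduled-testing rate, so the size is unknown. For entrants under Amendment 2 it mainly concerns those aged 12 or older. This is an inexpensive improvement to descriptive safety output, and it does not bear on the efficacy conclusions.

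**What to change.** - **SAP 5.4:** state that the analysis windows govern by-visit summaries only.
- **SAP 13.2:** add a by-arm shift table from baseline to the worst post-baseline value and grade (protocol Appendix 13), using all laboratory results after first application, whether scheduled, early termination, unscheduled or retest. For parameters graded in both directions, say that worst is taken separately for low and high. For parameters without a grade, use the normal range.
- **Amendment 4:** check whether it keeps the worst-grade shift. If it does, the new table delivers it. If it does not, the table is still worth having for the reason above.

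The data are already collected, and the SAP states that it was prepared before database lock and unblinding. The cost is a few sentences and one extra table per laboratory panel. The abnormality counts may look slightly less favourable than in the by-visit tables.
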